4.6.2. Adverse Events

A treatment-emergent adverse event (TEAE) is defined as an event that first occurred or worsened in severity after baseline. Pre-existing events will be considered to determine TEAE. The MedDRA Lowest Level Term (LLT) will be used in the Treatment-emergent computation. The maximum severity for each LLT during the baseline period will be used as baseline. The treatment period will be included as postbaseline for the analysis. For events with a missing severity during the baseline period, it will be treated as 'mild' in severity for determining treatment-emergence. Events with a missing severity during the postbaseline period will be treated as 'severe' and treatment-emergence will be determined by comparing to baseline severity. For events occurring on the day of first taking study medication, the start times of the study treatment and AE will be used to determine whether the event was pre-versus posttreatment. If start time for the AE is missing, it will be assumed to have started in the postbaseline period.

In an overview table, the number and percentage of participants with at least 1 TEAE, serious adverse event (SAE), fatal SAE, or discontinuation from study treatment due to an AE will be summarized. TEAEs (all and by maximum severity), SAEs, including deaths, and AEs that lead to treatment discontinuation will be summarized and analyzed by MedDRA system organ class (SOC) and PT or by PT alone. Potential AESIs will be summarized, which include:

See Section 4.6.2.1 for detailed description on AESI.

Summary tables as described in Table AMBZ.4.4 will be presented. Summary tables will include the number and percentage of participants reporting an event. For events that are gender-specific (as defined by MedDRA), the number of participants at risk will include only participants from the given gender. Listing of AEs may be provided as deemed appropriate.

Table AMBZ.4.4. Summary Tables Related to Adverse Events

Analysis		
Overview of AEs		
Summary of TEAE PTs by decreasing frequency		
Summary of TEAE PTs occurring in >=1% of participants by decreasing frequency		
Summary of TEAE PTs by decreasing frequency within SOC		
Summary of TEAE PTs by maximum severity by decreasing frequency within SOC		
Summary of SAE PTs by decreasing frequency within SOC		
Summary of fatal SAE PTs by decreasing frequency within SOC		
Summary of AEs leading to study treatment discontinuation by decreasing frequency of PTs within SOC		
Listing of SAEs		

[figure not shown]
Abbreviations: AE = adverse event; AESI = adverse event of special interest; PT = preferred term; SAE = serious adverse event; SOC = system organ class; TEAE = treatment-emergent adverse event.

[figure not shown]
4.6.2.1. Special Safety Topics including Adverse Events of Special Interest

This section includes areas of interest whether due to observed safety findings, potential findings based on drug class, or safety topics anticipated to be requested by a regulatory agency for any reason. In general, potential AESIs relevant to these special safety topics will be identified by one or more standardized MedDRA query(ies) (SMQs), by a Lilly defined MedDRA PT listing based upon the review of the most current MedDRA Version, or by TE relevant laboratory changes, as described below. Additional special safety topics may be added as warranted.

Unless otherwise specified, the treatment-emergent AESIs will be summarized for the safety population.

Full details of the search terms and rules for deriving AESIs in each of the sections below are described in the compound level safety standards along with information about the types of summaries and listings to be provided.

4.6.3. Clinical Laboratory Evaluations

As described more fully in compound level safety standards and in the laboratory-related PhUSE white papers [PhUSE 2013; PhUSE 2015], the clinical laboratory evaluations will be summarized with the following displays described in Table AMBZ.4.5:

Table AMBZ.4.5. Summaries/Displays/Analysis for Clinical Laboratory Evaluations

Analysis

Box plots of observed values (and change from baseline values) by visit. Change from baseline to last observation will be summarized within the box plot of changes (rightmost column), and descriptive summary statistics will be included in a table below the box plot.

Treatment-emergent abnormal high lab values (i.e., participants shifting from a normal/low maximum baseline value to a high maximum postbaseline.

Scatter plot of maximum (minimum) postbaseline value vs. maximum (minimum) baseline value if appropriate.

Shift tables showing the number of participants who shift from each category of maximum (minimum) baseline observation to each category of maximum (minimum) postbaseline observation. Here categories may be low, normal or high with cutoffs defined in the compound level safety standards.

For these displays, the postbaseline periods will be identical to those described in Table AMBZ.4.1. Postbaseline measurement for continuous analysis (e.g., boxplots) will include *only*

scheduled measurements, while postbaseline categorical analysis (e.g., shifts) will include *both* scheduled and unscheduled measurements.

For any lab performed on the day of first taking study medication at the start of the postbaseline period, the start time of the study treatment will be used to determine whether the lab was preversus postbaseline. If time for the lab is missing, it will be assumed to be in the baseline period (i.e., we assume the protocol-defined order of procedures was followed). Following the compound level safety standards, for some labs a safety concern may exist for only high (or only low) values. For these labs, displays with only maximum (or minimum) values will be used, and shift tables will be presented accordingly.

Hepatic serology, hematology, chemistry and coagulation tests will be done by local laboratory. Descriptive statistics of the test results will be summarized in a table. Summary will be done using standardized units (SI).

Screening assessment of Tuberculosis (TB) and evaluation of TB during the study will be listed, as appropriate.

4.6.4. Vital Signs and Other Physical Findings

As described more fully in compound level safety standards and in the vital signs-related PhUSE white papers [PhUSE 2013; PhUSE 2015], vital signs will be summarized similarly to the clinical laboratory evaluation (see Section 4.6.3). For vital signs, the low and high limits are based on a combination of a specified value and a change or percentage change. In this case, the PhUSE white paper recommends providing scatter plots and shifts to low/high. Boxplots will also be presented.

4.6.5. Electrocardiograms

Complete electrocardiogram (ECG) data will not be part of the clinical database for this study. Any clinically significant findings from ECGs that result in a diagnosis and that occur after the participant receives the first dose of the investigational treatment will be reported to Lilly or its designee as an AE via eCRF. Aside from standard AE summary tables no additional analysis of ECG data will be performed.

4.6.6. Immunogenicity

Compound level safety standards will be followed in the analyses of immunogenicity. Listings of immunogenicity assessments may be provided along with the summary of specified TEAEs by TE ADA status. The summary of TE ADA and NAb status may be produced as appropriate. Additional assessments of the relationship between immunogenicity and efficacy will be performed as deemed appropriate.

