Clinician-Administered		ents									I			
CCI	X													Complete on electronic tablet, by site staff trained on C-SSRS. See Section 8.2.6.1.
Baseline/Screening														

	I		I	I				Ш	I				IV	Comments
Visit number	1	2	3	4	5	6	7	8	9	10	ED	UV	801	Dosing visits: complete all visit activities before administration of mirikizumab.
Weeks from treatment assignment Study day														
Visit interval tolerance (days)														
Visit location	0	0	Т	0	0	О	О	О	О	0	0	0	Т	O = Onsite, T = Telephone
Physician's Global Assessment (PGA)		X				X				X	X			Complete on electronic tablet. See Section 8.1.3.
Laboratory Tests and S	ample Co	llection	ıs											
Hematology	X	X		X	X	X		X		X	X	X‡	X‡	† Optional per investigator discretion
Clinical chemistry	X	X		X	X	X		X		X	X	X‡	X‡	† Optional per investigator discretion
Urinalysis	X													
Serum pregnancy	X													For WOCBP. See Section 8.2.5.
Urine pregnancy (local)		X		X	X	X	X	X	X	X	X			WOCBP; negative test required prior to dosing at marked visits. See Section 8.2.5.
Follicle Stimulating Hormone (FSH)	Xŧ					Σ	ζ ‡							† Optional per investigator discretion, to confirm postmenopausal status. See Section 8.2.5.
Tuberculosis (TB) Testing	X									X^{Δ}				QuantiFERON®-TB Gold; central or local laboratory. See Section 8.2.7. ^Δ Visit 10: Perform only if necessary, per local requirements.
HIV screening test	X													

	I		I	I				III	[IV	Comments
Visit number	1	2	3	4	5	6	7	8	9	10	ED	UV	801	Dosing visits: complete all visit activities before administration of mirikizumab.
Weeks from treatment assignment														
Study day														
Visit interval tolerance (days)														
Visit location	О	0	Т	0	0	0	0	0	О	0	0	0	Т	O = Onsite, T = Telephone
Hepatitis C virus (HCV) screening tests	X													See Section 8.2.8.2.
Hepatitis B virus (HBV) screening tests	X													See Section 8.2.8.1.
HBV DNA						X		X			X	X		Only if positive serology at screening. See Section 8.2.8.1.
Immunogenicity (ADA) samples: predose		X												
Immunogenicity (ADA) samples		In	the eve	nt of C		elated e	vent- Co	ollect P	K and AD	A sample	es			Collect PK and ADA samples as detailed in Section 10.2.
Pharmacokinetic (PK) samples														
Stool Sample Collection	and Test	ing											_	
Dispense stool collection kit	X				X				X					V1 = 2 kits: Stool culture/ C difficile and fecal calprotectin V5/V9 = 1 kit: fecal calprotectin See Section 8.2.10.

	I		I	[Ш					IV	Comments

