8.4. Pharmacokinetics

In the event of a potential systemic drug hypersensitivity reaction or CCl related event, venous blood samples approximately concentrations of mirikizumab.

Collection, handling, and storage of samples

Instructions for the collection and handling of blood samples will be provided by the sponsor. The actual date and time (24-hour clock time) of each sampling will be recorded. Samples will be analyzed at a laboratory approved by the sponsor and stored at a facility designated by the sponsor. Serum concentrations of mirikizumab will be determined using a validated enzyme linked immunosorbent assay.

The sample retention is described in Section 10.1.12.

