8.8. Immunogenicity Assessments

In the event of a potential CC or an CC reaction and at visits and times specified in SoA (Section 1.3), venous blood samples will be collected to determine antibody production against mirikizumab. Additional samples may be collected at the final visit from participants who discontinued mirikizumab or were withdrawn from the study due to a CCI event or an CCI reaction.

Antibodies may be further characterized for their ability to neutralize the activity of mirikizumab.

To interpret the results of immunogenicity, a venous blood PK sample will be collected at the same time points to determine the concentrations of mirikizumab.

Sample retention is described in Section 10.1.12.

9. Statistical Considerations

The SAP will be finalized prior to first participant visit, and it will include a more technical and detailed description of the statistical analyses described in this section. This section is a summary of the planned statistical analyses of the most important endpoints, including primary and key secondary endpoints.

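### Does event-triggered ADA sampling call for a change to the optional immunogenicity displays in SAP 4.6.6?

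*SAP*

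**What the plan says.** **Analysis.** SAP 4.6.6 opens with a deferral: "Compound level safety standards will be followed in the analyses of immunogenicity". It then names three possible outputs beyond listings, each conditional:

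- TEAEs by ADA status: "Listings of immunogenicity assessments may be provided along with the summary of specified TEAEs by TE ADA status".
- Antibody status: "The summary of TE ADA and NAb status may be produced as appropriate".
- Efficacy: "Additional assessments of the relationship between immunogenicity and efficacy will be performed as deemed appropriate".

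SAP 4.1 adds that displays described in the plan need not all appear in the study report.

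**Sampling.** The main schedule (Protocol 1.3) has one scheduled row, "Immunogenicity (ADA) samples: predose", marked at Visit 2 only. The other ADA row in that schedule applies only if an event occurs, and so does the ADA row of the Continued Access schedule (Protocol 10.12.3). Protocol 8.8 calls for samples on a redacted event or reaction "and at visits and times specified in SoA (Section 1.3), venous blood samples will be collected to determine antibody production against mirikizumab". In the visible schedule the second part adds only Visit 2. Protocol 8.8 also allows final-visit samples, but only from participants who stopped because of the event. PK follows the same pattern: "To interpret the results of immunogenicity, a venous blood PK sample will be collected at the same time points". The visible trigger in Protocol 8.4 begins "In the event of a potential systemic drug hypersensitivity reaction" and continues to a second, partly redacted event type. Protocol 10.2.1 adds a follow-up sample after a suspected systemic hypersensitivity event, and its footnote says that a missed event sample is not a protocol deviation.

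**The concern.** Treatment-emergent ADA is a change from baseline, so it presumably needs a postbaseline sample. If such samples exist only after a triggering event, three things follow:

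- A TE-ADA count describes participants picked out by the event, not the study population.
- A table of TEAEs by TE-ADA status conditions on the type of event it is meant to compare.
- A comparison of efficacy by postbaseline ADA rests on a handful of selected participants.

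SAP 4.6.6 does not mention the selection, does not define the evaluable set, and does not say how participants without a postbaseline sample are classified. Counting them as negative would understate incidence and create a spurious link between ADA and the triggering events. A reader could then take such a table as a study-level finding about a biologic, where immunogenicity matters.

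**Working it through.** The plan states no ADA rate, trigger rate or immunogenicity sample size, so there is no figure to reproduce. The check has a textual part and an illustrative part.

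**Textual check**

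| Possible output | Sample needed | Who has it in the visible schedule | Event-selected? |
|---|---|---|---|
| Listing of ADA results | Any | All at Visit 2, plus participants with an event | No, if labelled by time |
| Baseline ADA against efficacy or TEAEs | Visit 2 predose | All participants | No |
| TE-ADA and neutralising-antibody summary | Postbaseline | Participants with a triggering event | Yes |
| TEAEs by TE-ADA status | Postbaseline | Participants with a triggering event | Yes |
| Postbaseline ADA against efficacy | Postbaseline | Participants with a triggering event | Yes |

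The selection problem is real for the last three rows and absent from the first two. SAP 4.6.6 speaks of immunogenicity and efficacy in general, so an analysis of baseline ADA fits its wording and is sound.

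**Illustration**

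Inputs: N = 160 (SAP 5). The trigger rates of 1%, 5% and 10% are assumptions.

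1. Expected number sampled, n = 160 × rate: 1.6 (taken as 2), 8 and 16. The chance that nobody is sampled is (1 − rate)^160, which is 0.20 at 1%, 0.0003 at 5% and about 0 at 10%.
2. Width of the worst-case bounds on the study-level TE-ADA proportion, (160 − n)/160: 158/160 = 98.75%, 152/160 = 95.0% and 144/160 = 90.0%. For example, 2 positives among 8 sampled is compatible with 2/160 = 1.25% up to (2 + 152)/160 = 96.25%.
3. Exact two-sided 95% upper limit within the sampled group when none is positive, 1 − 0.025^(1/n): 84.2% for n = 2, 36.9% for n = 8 and 20.6% for n = 16. With 2 of 8 positive, the exact interval is 3.2% to 65.1%.
4. Half-width of the 95% interval for an efficacy contrast, in outcome standard deviations, t × √(1/a + 1/b): 2.0 for 2 against 6 participants and 1.4 for 3 against 13.
5. Effect of selection, with true TE-ADA proportion p and event-risk ratio RR, both assumed: p·RR/(p·RR + 1 − p). For p = 5%, RR = 2 gives 0.10/1.05 = 9.5%, and RR = 5 gives 0.25/1.20 = 20.8%.

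These figures confirm that a TE-ADA table would be close to uninformative about the whole study. They do not show that the plan commits to such a table, or that it would count unsampled participants as negative.

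**The case for a change.** The best case for a change is that optional wording is a weak safeguard. It leaves the choice of display until the data are in, and SAP 4.6.6 carries no warning about selection. Compound-level standards can define a denominator but cannot supply samples that were never taken. One paragraph would settle the matter at almost no cost.

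The scientific part of this stands: TE-ADA incidence and its associations cannot be estimated for the study from event-triggered samples. The case for changing the plan does not:

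- The plan does not require any of the three displays. Omitting one that cannot be interpreted is already within its terms, and the listing that would replace it is already named.
- The rules for evaluability and for unsampled participants may well be in the compound-level standards. Those are not available here, so a missing rule cannot be shown.
- A misleading result needs two further steps: someone chooses to produce the table, and then either counts unsampled participants as negative or presents the subset as the study. The documents state neither.
- A blanket statement that associations of ADA with TEAEs or efficacy cannot be estimated would be wrong for baseline ADA, which is planned for all participants.

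A separate mismatch is sometimes raised alongside this one. SAP 4.7.1 assigns PK/PD analyses to a sponsor group, Protocol 9.3.6.2 plans no PK analysis, Protocol 8.5 says pharmacodynamics are not evaluated, and SAP 4.9 reports no departures from the protocol. That inconsistency is real but clerical. It changes no stated result and does not bear on ADA.

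**Conclusion.** No change to the plan follows. In the visible text, postbaseline ADA is event-triggered, so any TE-ADA display would describe an event-selected subset: about 2 to 16 of 160 participants if 1% to 10% have a trigger. The remaining detail is of the kind analysts fill sensibly. They would list the event-triggered results, use participants with a postbaseline sample as any denominator, and report the others as not evaluable. The outputs are optional, baseline ADA analyses are unaffected, and no primary or secondary result would differ.

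This rests on three assumptions: that the blank cells in the ADA row of the schedule are truly blank and not redacted, that treatment-emergent status needs a postbaseline sample (the definition is in standards not supplied), and that the trigger rates, which the documents do not give, lie near the illustrated range. The first two bear on whether the selection exists at all. The third affects only its size.

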4.6.7. Concomitant Therapy/ Procedure

Medications will be classified into anatomical therapeutic chemical (ATC) drug classes using the latest version of the World Health Organization (WHO) drug dictionary. Medication start and stop

dates will be compared to the date of first dose of treatment to allow medications to be classified as Concomitant for treatment period.

Prior medications are those medications that start and stop prior to the date of first dose of study treatment. Concomitant medications are those medications that start before, on or after the first dose of study treatment and end on or after the date of first dose of study treatment or are ongoing at the end of the study. If it cannot be determined whether a medication is concomitant or not due to a partial or missing date, the medication will be treated as concomitant.

Concomitant medications may be summarized by ATC and preferred term for the Safety Set and sorted by descending frequency. Prespecified concomitant therapy of acetaminophen/paracetamol may also be summarized.

Concomitant UC-related surgeries will be summarized by procedure type for the Safety Set, as needed. The other procedures including hepatic monitoring procedures and endoscopic procedures will be listed.

Prior and concomitant use of vaccines may be listed as appropriate.

4.6.8. Substance Use

Substance use of alcohol, caffeine, tobacco, nicotine, and recreational drug at screening and change in substance use by visit may be listed, as appropriate.

4.6.9. Extraintestinal Manifestations of Inflammatory Bowel Disease

Extraintestinal manifestations (EIM) of inflammatory bowel disease will be reported in the Inflammatory Bowel Disease (IBD) EIM eCRF by visit and will be summarized by prespecified term.

4.7. Other Analyses

Reference the analyses described in Appendix 5 in this section.

4.7.1. Other variables and parameters

The pharmacokinetic/pharmacodynamics (PK/PD) analyses will be conducted by the PK/PD and Pharmacometrics group at Eli Lilly.

4.7.2. Subgroup analyses

Subgroup analyses may be conducted for all primary and secondary endpoints in the FAS population. The subgroups to be analyzed are listed in Table AMBZ.6.3.

4.8 Interim Analyses

CCI

4.9 Changes to Protocol-Planned Analyses

There are no changes to the analyses described in the protocol.

5. Sample Size Determination

Approximately 160 participants will be assigned to study intervention. The sample size was determined by considering the precision of the estimated correlation between endpoints. Simulations were performed for both binary and continuous measures where the true correlation varied between CCI . The average half width of the 95% CI for the correlations at Week varied between under considered assumptions for an overall sample size of 160. The average half width of the 95% CI varied between for endpoints during the maintenance period under the assumption that CCI of participants could discontinue early from the study.

Additionally, the proposed sample size of 160 participants is considered sufficient to have power to detect a significant (non-zero) change from baseline in UNRS at Week (primary endpoint).

6. Supporting Documentation

6.1. Appendix 1: Description and Derivation of Efficacy and Health Outcome Endpoints

[figure not shown]
All binary endpoints will be coded as Yes/No, unless otherwise specified.

[figure not shown]
Table AMBZ.6.1. Description and Derivation of Efficacy, Safety and Health Outcomes Measures and Endpoints

[figure not shown]
Measure	Description	Variable	Derivation / Comment	Definition of Missing
Mayo Score and components	The Mayo score is a composite instrument to measure Ulcerative Colitis disease activity. It is comprised of the following 4 subscores:	SF subscore		
		RB subscore		
		ES subscore		

Measure	Description	Variable	Derivation / Comment	Definition of Missing
	CCI	PGA subscore		
		Clinical Remission		
		Alternate Clinical Remission		
		Modified Mayo Score	_	
		(MMS)		
		Clinical Response		
		Symptomatic Remission	_	
		Symptomatic Remission		
		SF component of	_	
		clinical remission RB component of	_	
		clinical remission		

[figure not shown]
Measure	Description	Variable	Derivation / Comment	Definition of Missing
		Endoscopic Normalization Absolute SF		
		Endoscopic Remission		
Urgency NRS	The Urgency numeric rating scale (NRS) is a single item that measures the severity for the urgency (sudden or immediate need) to have a bowel movement in the past 24 hours using	Urgency NRS		
	an 11-point NRS ranging from 0 ("no urgency") to 10 ("worst possible urgency").	Change from Baseline Urgency NRS		
		Urgency NRS CMI (>=3 Point Improvement)		
		Alternate Urgency NRS Remission		
		Urgency NRS Remission		

[figure not shown]

[figure not shown]

[figure not shown]

[figure not shown]
Measure	Description	Variable	Derivation / Comment	Definition of Missing
		Normal Number of Stools	Use the single item collected	CCI
		CCI	Use the single item collected	-
		CCI	CCI	
		CCI	CCI	

[figure not shown]

